Appendix E Appendix F	Unacceptable methods of contraception language around barrier methods modified	Clarification
Appendix H	New appendix with information on P-gp and CYP3A4 inducers/inhibitors	Background on exclusion criteria surrounding the use strong inducers or moderate to strong inhibitors of CYP3A4 or strong inhibitors or inducers of P-glycoprotein for Parts D and E

Summary of Changes in Amendment 8

Section(s)	Change	Rationale
Synopsis, Section 2	
Modified the following primary objective:
 
 Identify the maximum tolerated dose (MTD) and/or optimal dose and schedule of SEA-BCMA monotherapy, and in combination with dexamethasone, in subjects with RRMM 
Removed the following primary objective:
 
 Evaluate the safety and tolerability of SEA-BCMA in combination with nirogacestat and dexamethasone in subjects with RRMM 
Removed the following exploratory objective:
 
 Assess the PK of nirogacestat in combination with SEA-BCMA and dexamethasone. 
Modified the following exploratory objective:
 
 Assess impact of SEA-BCMA in combination with standard of care therapies and SEA-BCMA in combination with nirogacestat and dexamethasone on health-related quality of life (HRQoL) from the subject's perspective. 	Reflects modified study design
Synopsis	
Study population for Parts B and C modified as follows: In Parts B, and C, and E, subjects must not have other therapeutic options known to provide clinical benefit in multiple myeloma available, must have received at least 3 prior lines of antimyeloma therapy, and must be refractory to at least 1 agent in each of the following classes: PI, IMiD, and an anti-CD38 antibody.
	Aligned with wording in Section 4 for clarity
Synopsis, Sections 3, 9.1, 9.3.10, Figure 1	
Study design and statistical methods updated to reflect the following changes to expected sample sizes:
 
Up to approximately 305131 subjects are expected to be enrolled in this study. This number is based on the following assumptions:
 
 Up to approximately 6545 subjects will be evaluated in Part A (monotherapy dose- escalation and expansion; every 2 weeks [q2wk] dosing). Up to approximately 4020 subjects will be evaluated in Part B (monotherapy intensive dosing; once weekly [q1wk] for 8 weeks, followed by q2wk dosing). Up to approximately 8060 subjects total will be evaluated in the Part C dexamethasone combination therapy cohorts (up to 4020 in each of 2 optional cohorts). Up to 20 subjects will be enrolled in cohort 1 (standard dosing SEA-BCMA). Up to 40 subjects will be enrolled in cohort 2 (intensive dosing 	To reflect change in sample size for Parts A, B, C, and D; and removal of Part E.

Section(s)	Change	Rationale
	
SEA-BCMA): 20 subjects in each of up to 2 parallel dose levels.
 
 Up to approximately 806 DLT-evaluable subjects total will be evaluated in the Part D pomalidomide and dexamethasone combination cohorts (up to 40 in each of 2 optional cohorts safety run-in cohort). 	
Synopsis, Section 4.1	
Part D inclusion criterion 2c and corresponding text in synopsis revised require that subjects have received 3 or more prior lines of therapy, and remove prohibition of prior pomalidomide therapy:
 
In Part D, subjects must have not received prior pomalidomide, must have received at least 2³ prior lines of antimyeloma therapy, including at least 2 consecutive cycles of both lenalidomide and a PI (given separately or in combination)^{a PI, IMiD, and an anti-CD38 antibody}, and must have documented International Myeloma Working Group (IMWG) disease progression on or within 60 days of completion of their last treatment.
	Reflects modified study design
Synopsis, Figure 1, Sections 3.1, 3.3.1.2, 4, 6.5.3, 9.1	Removed Part D Cohort 2; modified Part D cohort 1 to a 6-subject safety run-in.	Reflects modified study design
Synopsis, Figure 1, Sections 1.6.2, 3.1, 3.3.1.2, 4, 5.3.3, 5.5, 5.6.2, 5.6.3, 5.7, 6, 7.3, 7.7.9, 9.1, 9.3.1.7.3, Appendix E	Removed Part E (SEA-BCMA in combination with nirogacestat and dexamethasone)	Reflects removal of Part E
Section 3.1.2	
Removed the following text:
 
Initially, up to 20 subjects may be enrolled in Part B; an interim futility analysis will be performed after 20 subjects are efficacy-evaluable at optimal dose to determine whether the cohort may be expanded up to 40 subjects
	To reflect Part B sample size of 20 subjects
Appendix A, B	
Removed schedule of events and sample collection schedule for Part E.
 
Removed assessments specific to Part D Optional Cohort 2.
	Reflects modified study design
Appendix H	Removed list of p-gp and CYP3A inhibitors and inducers. List was applicable only to nirogacestat (Part E).	Does not apply; Part E/nirogacestat removed from study design.

Summary of Changes in Amendment 9

Section(s)	Change	Rationale
Section 1.1	Updated the description of current treatment landscape	To reflect current treatment landscape in the US and Europe
Section 1.6.1	Discussion and Rationale for Study Design was moved from Section 3.2 to Section 1.6.1.	Consolidate related information
Section 1.6.3.3	Added section for Patient Input Into Design	Further details on study
Section 1.7	Added section for Benefit/Risk Assessment	Improve subject safety
Section 3.1.1	Removed the following text from Section 3.1.1.1: Subjects may continue on treatment until progressive disease (PD) or unacceptable toxicity, whichever occurs first.	Moved to Section 3.1.4
Synopsis and Section 3.1.3.3 Section 4.1 Section 4.3.1	Clarified that Part D will enroll subjects in the US only.	Clarification
Sections 3.1.4	Added Section 3.1.4 to capture duration of treatment information for all cohorts in one location.	Clarity of treatment duration
Section 3.1.6.1	Added Section 3.1.6.1 to detail when enrollment will be paused at the cohort level.	Improve subject safety
Section 3.1.6.2	Added the following bolded text and removed text in strikethrough in Section 3.1.6.2 Enrollment Halt for the Entire Study: Enrollment in the entire study will be halted by the sponsor if the overall benefit-risk balance is considered unfavorable. Stopping criteria will be continuously monitored throughout the study by the sponsor in consultation with the SMC, considering enrollment halt if the incidence and/or the severity of toxicity leads to a risk-benefit assessment that is unacceptable to the study population. The sponsor will consult the SMC to consider whether to allow subjects already receiving treatment to continue, to consider modifying the protocol to continue the trial, or to terminate the study. If enrollment is halted due to safety concerns, enrollment can only be restarted after appropriate amendments and notifications to Regulatory Authorities, with approval to resume, if required by local regulations In the event there is a recommendation to amend the protocol to continue, regulatory authorities will be consulted.	Improve subject safety
Section 3.1.8	Section added to describe study close	Clarify study duration
Section 4.1	Inclusion Criterion 2b for Parts B and C was revised to add: Prior BCMA-directed myeloma therapy, excluding prior treatment with SEA-BCMA, is permitted (eg, ADC, CAR-T cell therapy, or bispecific antibody targeting BCMA) provided that at least 3 months will have elapsed from the last dose of prior BCMA targeting therapy and	Change in treatment landscape of RRMM

Section(s)	Change	Rationale
	Cycle 1 Day 1 of this study, and that the subject has recovered from any clinically significant toxicity of the prior BCMA-targeting therapy.	
Section 4.2	Exclusion Criterion 1 modified, with deletions shown in strikethrough text: Parts A , B, C, and D: Prior exposure to any other BCMA-directed therapy	Change in treatment landscape of RRMM
Section 5.1	Added the following bolded text to Treatments Administered: SEA-BCMA is a non-fucosylated monoclonal antibody directed against BCMA. Subjects will receive the investigational medicinal product SEA-BCMA as monotherapy or combination therapy (Section 3.1). Subjects in combination therapy cohorts will also receive dexamethasone or dexamethasone plus pomalidomide. Guidance for intrasubject dose-escalation for subjects who have the potential to achieve greater benefit at a dose higher than the dose level assigned during dose-escalation is described in Section 5.2.3.	Clarify treatment regimens
Section 5.2.7	Section added regarding access to study drug after the end of the study.	Clarify duration of access to study drug
Section 5.3.2	Dexamethasone method of procurement modified with new text in bold and deleted text in strikethrough: In the US, dexamethasone will be sourced by study sites from commercial supply. In other countries, oral dexamethasone will be provided to the study sites by the sponsor or dexamethasone (oral or IV) will be sourced by study sites from commercial supply. Dexamethasone is commercially available and approved by the US FDA. Dexamethasone will be supplied by the study site and billed to subjects and/or their third party payer (insurance, a healthcare provider, or applicable government program).	Reflect regional variability
Section 5.4.2	Pomalidomide method of procurement modified with new text in bold and deleted text in strikethrough: In the US, pomalidomide will be sourced by study sites from commercial supply. Pomalidomide is commercially available and approved by the US FDA. Pomalidomide will be supplied by the study site and billed to subjects and/or their third party payer (insurance, a healthcare provider, or applicable government program).	Reflect regional variability
Section 6	Skeletal survey defined as: via whole body plain film radiography, or via whole body computed tomography [CT] scan, to assess presence and size of lytic bony lesions	To add definition of study assessment
Sections 6, 7.1, 7.2, Appendix A	Added detail in bold to indicate plasmacytoma scans will be conducted: per institutional standard imaging modality	To add definition of study assessment
Synopsis, Sections 6.4.4, 6.5.4, 7.3	Indicated that qualitative interviews will be conducted in 10 subjects total from Part C and Part D.	Clarification

Section(s)	Change	Rationale
Appendix A	Part C Schedule of Events: removed footnote DD “24-hour urine collection required if UPCR >2 mg/mg”	Correction
Appendix B	Part D Schedule of Events footnotes C and P were redundant, so footnote P was replaced with footnote C.	Correction
Appendix B	Pharmacokinetic, immunogenicity, and biomarkers sample collection tables for Parts B, C and D modified to remove peripheral blood immunophenotyping sample collection.	To reflect updated sample collection requirement
Throughout	Minor corrections and clarifications	Corrections and clarifications

IDI	Intended dose intensity
IMiD	immunomodulatory drug
IMWG	International Myeloma Working Group
IRR	infusion-related reaction
IV	intravenous
LLOQ	lower limit of quantification
MedDRA	Medical Dictionary for Regulatory Activities
MM	multiple myeloma
MMAE	monomethyl auristatin E
MTD	maximum tolerated dose
mTPI	modified toxicity probability interval
NCI CTCAE	National Cancer Institute Common Terminology Criteria for Adverse Events
ORR	objective response rate
OS	overall survival
PAVA	Pool-Adjacent-Violators Algorithm
PD	progressive disease
PFS	progression-free survival
PI	proteasome inhibitor
PK	pharmacokinetic
PR	partial response
RDI	Relative dose intensity
RRMM	relapsed or refractory multiple myeloma
q3wk	once every 3 weeks
sCR	stringent complete response
SAE	serious adverse event
SAP	statistical analysis plan

SD stable disease
SMC Safety Monitoring Committee
UPC urine protein to creatinine
UPM unit probability mass
VGPR very good partial response

1 INTRODUCTION

This document outlines the statistical methods to be implemented within the scope of Protocol SGNBCMA-001, entitled 'A phase 1 study of SEA-BCMA in patients with relapsed or refractory multiple myeloma'. Results of the proposed analyses will become the basis of the clinical study report for this protocol.

The purpose of this plan is to provide specific guidelines from which the analysis will proceed. All planned analyses specified in this document will be performed. Any changes to this plan, in the form of "post hoc" or "data driven" analyses will be identified as such in the final clinical study report. Any changes will either be reflected in amendments to this plan before the database lock or specifically documented in the clinical study report.

2 STUDY OBJECTIVES AND CORRESPONDING ENDPOINTS

This study will evaluate the safety and antitumor activity of SEA-BCMA in patients with RRMM. Specific objectives and corresponding endpoints for the study are summarized below in **Error! Reference source not found..**

Table 1: Objectives and corresponding endpoints

Primary Objectives	Corresponding Primary Endpoint
Evaluate the safety and tolerability of SEA-BCMA monotherapy in subjects with relapsed or refractory multiple myeloma (RRMM)	Type, incidence, severity, seriousness, and relatedness of adverse events (AEs)
Identify the maximum tolerated dose (MTD) and/or optimal dose and schedule of SEA-BCMA monotherapy, and in combination with dexamethasone, in subjects with RRMM	Type, incidence, and severity of laboratory abnormalities Incidence of dose-limiting toxicities (DLTs)
Evaluate the safety and tolerability of SEA-BCMA in combination with SOC therapies in subjects with RRMM	
Secondary Objectives	Corresponding Secondary Endpoints
Identify a recommended single-agent dose and schedule of SEA-BCMA	Incidence of DLTs, cumulative safety and activity by dose level and schedule
Assess the pharmacokinetics (PKs) of SEA-BCMA	Maximum serum concentration and area under the serum concentration-time curve
Assess the immunogenicity of SEA-BCMA	Incidence of SEA-BCMA antitherapeutic antibodies (ATA)
Assess the antitumor activity of SEA-BCMA	Best response per the International Myeloma Working Group (IMWG) uniform response criteria (Kumar 2016) Objective response rate (ORR) Duration of objective response (OR) and complete response (CR) Progression-free survival (PFS) Overall survival (OS)
Exploratory Objectives	Corresponding Exploratory Endpoints
Study SGNBCMA-001 in document. 15-Aug-2023 SEA-BCMA	Statistical Analysis Plan Version Error! No text of specified style

Assess incidence and level of BCMA expression in RRMM and relationship to clinical response to SEA-BCMA	Characterization of BCMA expression on malignant plasma cells
Assess the pharmacodynamic effects and biomarkers of response, toxicity, and resistance to SEA-BCMA	Exploratory biomarkers of SEA-BCMA mediated pharmacodynamic effects
Assess minimal residual disease (MRD) in subjects with very good partial response (VGPR) or better	Rate of MRD clearance
Assess impact of SEA-BCMA in combination with SOC therapies on health-related quality of life (HRQoL) from the subject's perspective.	Descriptive outcomes of qualitative interviews
	Maximum serum concentration and area under the serum concentration-time curve

3 STUDY DESIGN

This is a phase 1, open-label, multicenter, dose-escalation study designed to evaluate the safety, tolerability, and antitumor activity of SEA-BCMA monotherapy and combination in adults with RRMM. The study will be conducted in 4 parts:

Part A: Monotherapy dose-escalation and expansion

Dose-escalation: Up to approximately 25 subjects will be treated with SEA-BCMA monotherapy q2wk to evaluate the safety and tolerability of SEA-BCMA, and to identify the MTD or optimal dose.

Expansion: Up to approximately 20 subjects will be treated with SEA-BCMA monotherapy at dose levels not exceeding the MTD or optimal dose to further characterize the safety and antitumor activity of SEA-BCMA.

Part B: Monotherapy intensive dosing. Up to 20 subjects will be treated at the recommended dose in an expansion cohort testing weekly induction dosing (q1wk) of SEA-BCMA for 8 weeks, followed by q2wk maintenance dosing. This expansion cohort will begin with a 6-subject safety run-in with dose de-escalation permitted.

Part C: Dexamethasone combination therapy cohorts. Up to approximately 60 subjects may be enrolled to evaluate the safety and antitumor activity of SEA-BCMA in combination with dexamethasone.

Cohort 1: The standard dosing combination cohort will combine dexamethasone with SEA-BCMA administered q2wk. This expansion cohort will begin with a 6-subject safety run-in with dose de-escalation permitted. Cohort expansion up to 20 subjects may occur, if permitted after completion of the safety run-in.

Cohort 2: The intensive dosing combination cohort will combine dexamethasone with SEA-BCMA administered q1wk for 8 weeks, followed by q2wk dosing. This expansion cohort will complete a 6-subject safety run-in at 800 mg SEA-BCMA intensive dosing (dose level -1) and, if deemed tolerable, will be followed by a 6-subject run in at 1600 mg SEA-BCMA intensive dosing. Cohort expansion up to a total of 20 subjects may occur in each of up to 2 dose level cohorts, eg, 800 mg and 1600 mg SEA-BCMA dose levels, if permitted after completion of each safety run-in.

Part D: Pomalidomide and dexamethasone combination therapy cohort. Up to 6 DLT evaluable subjects may be enrolled in this safety run-in cohort to evaluate the safety of

SEA-BCMA administered q2wk in combination with pomalidomide and dexamethasone. Part D will be conducted in the US only.

Cohort 1: The standard dosing combination cohort will combine dexamethasone and pomalidomide with SEA-BCMA administered q2wk. This expansion cohort will begin with a 6-subject safety run-in with dose de-escalation permitted.

A Safety Monitoring Committee (SMC) consisting of the study medical monitor, drug safety representative, site investigators, and the study biostatistician will monitor the safety of subjects and make dosing recommendations throughout dose-escalation, dose-expansion, post-remission treatment, and combination therapy treatment. The SMC may recommend investigation of an intermediate dose level or an alternative dosing schedule if warranted by cumulative safety and PK/pharmacodynamic data.

The dose-escalation part of SEA-BCMA monotherapy will be conducted in up to approximately 25 subjects using the modified toxicity probability interval (mTPI) method ([Ji 2010](#)) to evaluate safety and tolerability, and to identify the MTD of SEA-BCMA. If the MTD is not reached, safety, PK, pharmacodynamic, and biomarker analyses, as well as preliminary antitumor activity, will be used to determine the optimal dose. De-escalation to a lower dose level may be performed at any time by the sponsor in consultation with the SMC. Intrasubject dose-escalation to a dose level shown to be safe may be permitted in the event that a subject has not experienced a Grade ≥ 2 adverse event (AE) while on study treatment, has received at least 1 cycle of SEA-BCMA at the current dose level, and achieves stable disease (SD) or better.

4 ANALYSIS SETS

This section defines each of the analysis sets that will be utilized. The use of each analysis set will be discussed in Section 6.

4.1 All Treated Patients Analysis Set

The All Treated Patients set includes all patients who receive any amount of SEA-BCMA. The All Treated Patients set will be used for presentation of safety data and efficacy endpoints.

4.2 DLT Evaluatable (DE) Analysis Set

The DLT-evaluative (DE) analysis set will include all treated patients who either (1) experience a DLT, or (2) receive at least 75% of the intended SEA-BCMA dose and are followed for the full DLT evaluation period. The DLT evaluation period is defined as cycle 1 of treatment. For q2wk schedule, cycle 1 includes the first 2 doses of treatment. Patients will be replaced for DLT evaluation if they received prohibited medications (as described in protocol Sections 5.4.2 and 5.4.3), or are deemed inevaluable for clinical reasons by the SMC. Patients on the q2wk dosing schedule who receive only the 1st dose during cycle 1 for reasons other than toxicity may not be DLT-evaluative and will be replaced.

4.3 All Screened Patients Analysis Set

The all screened patients analysis set includes all patients who sign informed consent.

4.4 All Enrolled Patients Analysis Set

The all enrolled patients analysis set includes all patients enrolled in the study. A patient is considered enrolled if he/she has met all criteria for participation in the study and has Seattle Genetics approval as documented in the eCRF.

5 STATISTICAL CONSIDERATIONS

5.1 General Principles

This is a phase 1 dose-escalation study. All analyses will be descriptive; however, confidence intervals may be presented to describe precision of estimates.

Descriptive statistics (mean, median, standard deviation, minimum, and maximum) will be used to summarize continuous variables. Frequencies and percentages will be used to summarize categorical variables. The two-sided 95% exact confidence interval using Clopper-Pearson methodology ([Collett 1991](#)) will be calculated for the response rates where applicable (e.g., ORR).

The median survival time will be estimated using the Kaplan-Meier method; the associated 95% confidence interval (CI) will be calculated based on the complementary log-log transformation ([Collett 1994](#)).

Unless otherwise specified, data are to be summarized by dose level and overall. DLT summarization will only include patients in the dose escalation part of the study, and will be done by dose level. For all other analyses, patients treated in the dose escalation part of the study may be pooled together with patients treated at the same dose level in the expansion cohorts.

Any analysis not described in this plan will be considered exploratory, and will be documented in the clinical study report (CSR) as a post hoc analysis or a change to the planned analysis.

To comply with regulatory electronic submission guidelines, listings of all clinical data will be submitted as electronic data sets. To facilitate data review for the study report, only pertinent data listings will be created and attached to the appendix of the CSR. All statistical output will be produced using SAS[®], version 9.3 or more recent. Other statistical software, if used, will be described in the clinical study report.

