9.3.9.3. Dose-Limiting Toxicity

The observed number and proportion of subjects experiencing a DLT will be reported for the dose-escalation part.

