6.6.2 Dose-Limiting Toxicity

The observed number and proportion of patients experiencing a DLT will be reported for the dose escalation part of the study. At each dose level, model-based estimates of the probability of DLT will be presented along with the corresponding 95% credible intervals.

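### DLT number and proportion are planned for Part A dose escalation only, so none of the Part B, C and D run-ins has a planned DLT n/N on the DLT-evaluable set

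*SAP*

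**What the plan says.** The general rule in SAP 5.1 is "DLT summarization will only include patients in the dose escalation part of the study, and will be done by dose level". The specific section, SAP 6.6.2, repeats it: "The observed number and proportion of patients experiencing a DLT will be reported for the dose escalation part of the study". It then adds, "At each dose level, model-based estimates of the probability of DLT will be presented along with the corresponding 95% credible intervals". Protocol 9.3.9.3 has one sentence: "The observed number and proportion of subjects experiencing a DLT will be reported for the dose-escalation part".

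Table 1 (SAP 2; also protocol 2) lists DLT incidence as a primary endpoint and does not limit it to any Part. One primary objective reads "Identify the maximum tolerated dose (MTD) and/or optimal dose and schedule of SEA-BCMA monotherapy, and in combination with dexamethasone, in subjects with RRMM". Another covers safety and tolerability in combination with standard-of-care therapies. A secondary endpoint is "Incidence of DLTs, cumulative safety and activity by dose level and schedule".

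Protocol 3.1.2, 3.1.3.2 and 3.1.3.3 set up 6-subject DLT run-ins in Parts B, C and D. SAP 4.2 defines the DLT-evaluable set over all treated patients, not over Part A alone. SAP 4 says that Section 6 will explain how each set is used, but Section 6 never names the DLT-evaluable set. SAP 8 lists the changes from the protocol and from the original SAP. None of them extends the DLT summary to the run-ins.

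**The concern.** The endpoint and the analysis have different scopes. The endpoint serves objectives about schedule and the combinations, while its only specified number and proportion stop at the Part A escalation. The regimens left out are the ones added after Part A, namely weekly dosing, dexamethasone, and pomalidomide with dexamethasone. For each of these a DLT count is the decision variable. In the de-escalation branch of Part C, that count also declares an MTD for the combination, which is a named primary objective.

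At stake is whether the study report carries a pre-planned DLT rate for any weekly or combination regimen. If the SAP is followed literally, it does not. If such a table is added later, SAP 5.1 classes it as exploratory and requires it to be documented as post hoc or as a change to the plan. That is an odd status for a primary endpoint. With 6 subjects per run-in, a reader also needs the count and its denominator, because a statement that a regimen was tolerable does not convey how little data lies behind it.

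**Working it through.** **1. What the dose-escalation part means.** SAP 3 and protocol 3.1.1.1 use the term for the Part A monotherapy mTPI stage of up to about 25 subjects. SAP 3 calls Part B, both Part C cohorts and the Part D cohort expansion cohorts. The SAP 5.1 limit therefore excludes them.

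**2. Planned total.** The documents give 131. The parts sum to it: A 45 + B 20 + C 60 + D 6 = 131. No planned figure is in dispute here.

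**3. Run-ins outside the planned DLT summary** (protocol 3.1.2, 3.1.3.2, 3.1.3.3):

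| Run-in | SEA-BCMA regimen | What the DLT count decides | Evaluable N |
|---|---|---|---|
| Part B | 1600 mg weekly, then q2wk | 0–1 of 6: expand; 2 or more: de-escalate | 6 |
| Part C Cohort 1 | 1600 mg q2wk + dexamethasone | same rule; lower level can be declared MTD | 6 |
| Part C Cohort 2, lower | 800 mg weekly, then 1600 mg q2wk + dexamethasone | 3-subject look, then 6 | 6 |
| Part C Cohort 2, upper | 1600 mg weekly, then q2wk + dexamethasone | 6-subject rule | 6 |
| Part D | 1600 mg q2wk + pomalidomide + dexamethasone | at most 1 of 6: tolerable | 6 |

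The sum is 6 + 6 + 6 + 6 + 6 = 30 evaluable subjects, of whom 6 + 6 + 6 = 18 are on the weekly schedule. One de-escalation in Part B and one in Part C Cohort 1 would give 30 + 6 + 6 = 42. The documents do not state these totals; they follow from the run-in rules. Against about 25 escalation subjects, 30/(30 + 25) = 55% of planned DLT assessments have no planned n/N.

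**4. Whether SAP 6.6.1 supplies the figure.** Its list of adverse event summaries includes one for events classed as DLTs. Under SAP 6.6 and 6.6.1 it is by preferred term, by dose level and total, on All Treated patients. There are two readings:
- SAP 5.1 governs it, in which case it contains escalation patients only.
- SAP 5.1 does not govern it, in which case the two sections conflict, and the table still uses a different denominator and does not isolate a run-in.

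The denominator matters. Suppose 2 subjects have DLTs in a cohort that ends with 20 subjects. On the 6 run-in subjects the result is 2/6 = 33.3% (exact 95% CI 4.3–77.7%). On All Treated it is 2/20 = 10.0% (1.2–31.7%).

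**5. Whether naming the DLT-evaluable set is enough.** It is not. SAP 4.2 admits any treated patient who has a DLT or completes Cycle 1 with enough dose. Subjects 7 to 20 of an expanded cohort can therefore belong to it, so N has to be defined.

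**6. Precision of one run-in** (Clopper-Pearson, 95%). For 0/6 the upper limit is 1 − 0.025^(1/6) = 0.459. From the beta quantiles, 1/6 gives 0.4–64.1% and 2/6 gives 4.3–77.7%.

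**The case against.** The best reply is that run-in DLTs are neither ignored nor necessarily unreported. Protocol 3.1.9.2 has the SMC determine DLTs in the run-ins of Parts B, C and D. Protocol 9.3.1.7.3 assigns the DLT-evaluable set to determination of the MTD, without limiting this to Part A. SAP 6.6.1 lists a summary of adverse events classed as DLTs, and all adverse events are listed. Every analysis is descriptive, so calling an added table a change to the plan affects no inference.

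Much of this stands, and it bounds the point. A reader might infer that the run-ins are not monitored for DLTs, or that the report would contain no trace of a DLT from Parts B to D. The documents support neither: SMC review is specified, and planned adverse event output may show the events. What the reply does not provide is a planned number and proportion per run-in on the evaluable subjects. SMC review is operational. The protocol sentence on the MTD names a set for a decision, not a table. The adverse event summary has the wrong denominator and is itself in doubt under SAP 5.1. The descriptive nature of the study does not help either, since a descriptive n/N is the missing item.

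It is also fair that 30 is conditional. Cohorts may not open, and Cohort 2 can stop after 3 subjects.

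**Conclusion.** The point holds in this form: SAP 5.1, SAP 6.6.2 and protocol 9.3.9.3 expressly confine the DLT number and proportion to the Part A escalation. No DLT n/N on the DLT-evaluable set is therefore planned for any of the 5 run-ins. This is a stated exclusion, not just missing detail, and it affects a primary endpoint for every weekly and combination regimen. Its size is 30 evaluable subjects, assuming that all run-ins open, complete at 6 and do not de-escalate.

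The defect is one of reporting. It does not affect how the run-ins are conducted or decided, and it gives no ground to question the run-in rules themselves. It should be corrected, and the correction is small.

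**What to change.** In the SAP:
- Delete the escalation-only limit in 5.1 and 6.6.2.
- In 6.6.2, name the DLT-evaluable set. Report DLT n/N for Part A by dose level and for each run-in by Part, cohort, schedule and dose level, including any de-escalated level.
- Define N for a run-in as the DLT-evaluable subjects on whom its decision was made (the first 6, after replacement of non-evaluable subjects). If Cohort 2 stops at its 3-subject look, show that N. Show any later evaluable subjects separately.
- State that the 6.6.1 summary of adverse events classed as DLTs covers all Parts.
- Keep the Part A model-based estimates and credible intervals as planned. An exact CI per run-in is optional (0/6: 0–46%; 1/6: 0.4–64%; 2/6: 4–78%).
- Record the departure from protocol 9.3.9.3 in SAP 8.1.

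No protocol amendment is needed, since protocol 9.3 requires one for analysis methods only when site conduct changes, and here it does not. If the database is already locked, SAP 1 provides for documenting the change in the study report. The cost is SAP wording and a table shell, with no new data or patients.
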